Assignment to Study Group: Participating children and their primary caregivers will be assigned to one of three groups. Participants will be stratified by age (18-35 months; >36 months) and developmental quotient (DQ<55; DQ ≥55) at project enrollment, prior to being randomized. After stratification, participants will be randomly assigned to the one of the three groups using random permuted blocks of 6. This approach has been shown to yield groups that are closely balanced with regard to size and relevant pre-treatment characteristics. All pre-treatment assessments will be collected prior to randomization to prevent bias during testing based on knowledge of future group placement.

b. Sources of Materials

The sources of data for this study will include: (1) direct assessment of child functioning using standardized assessments; (2) completion of standardized questionnaires by parents; (3) written survey completion by parents; and (4) videotaped coding of treatment processes. All data will be used exclusively for research purposes. All surveys and interviews will use codes rather than subject names. Only the PI and primary research team members will have access to subject identities. Procedures to minimize risk of loss of confidentiality are presented below.

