Parent Measures: Parents will complete the Parenting Sense of Competence Scale at pre-treatment, post-treatment, and follow-up to assess parent self-efficacy. Using the videotapes of the parent-child interaction in the home at pre-, post-treatment, and follow-up, the research team will assess parent use of the intervention strategies. Parents will also be asked to provide demographic information and complete the Parent Expectancies for Therapy Scale, a measure of treatment expectancy, the Computer-Email-Web Fluency Scale, a measure of computer/internet fluency, at pre-treatment, and the Parenting Stress Index, a measure of parenting stress at pre-treatment. Parents will be asked to complete the Treatment Evaluation Inventory, measure of treatment acceptability, at the conclusion of treatment. Parents will complete the Additional Services Form to monitor the type and number of hours per week of all non-study treatments once per month throughout study participation.

c. Potential Risks

There are no known serious health or psychological risks related to participation in this study. Procedures to minimize risk of loss of confidentiality are presented in the following section. In addition, there are legal limits to the confidentiality of information obtained during the research study. All information obtained from participants will be held confidential unless there is serious threat of harm to a child or to self or others. These limitations will be addressed in the consent forms. Collection of data from participants will include standardized child assessment measures, standard parent questionnaires regarding their child's development and behavior, standard parent questionnaires about their well-being and satisfaction with treatment, and videotape recordings. Precautions will be applied to all collected data from these activities, which will be stored in a private, secure and confidential location at MSU. All participants will be made aware of how collected data will be handled.

Adequacy of Protection Against Risks

a. Recruitment and Informed Consent

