Aim 3: To examine whether pre-treatment parenting stress moderates the effects of *ImPACT Online* on parent fidelity and parent self-efficacy at post-treatment. Pre-treatment parenting stress will be included in the MLM models as a covariate. The pre-treatment parenting stress by time interaction will be used to determine whether pre-treatment parenting stress moderates change over time, irrespective of treatment group. The three-way interaction of pre-treatment parenting stress, group, and time will be used to examine whether the relationship between group assignment and change over time (i.e., group slopes) varied by pre-treatment parenting stress. A significant interaction will be followed up by simple slopes analyses.

Aim 4: To examine whether gains in parent fidelity (or parent self-efficacy) and child intentional communication at post-treatment mediate the effects of the *ImPACT Online* on child verbal language at the 3-month follow-up. We will conduct two serial mediation analyses using the PROCESS macro in SPSS to examine whether gains in parent fidelity (Mediator 1) and child intentional communication (Mediator 2) at post-treatment mediate the effect of *ImPACT Online* in child outcomes at follow-up. A second serial mediation analysis will be conducted to examine whether gains in parent self-efficacy (Mediator 1) and child intentional communication (Mediator 2) at post-treatment mediate the effect of *ImPACT Online* in child outcomes at follow-up.

Aim 5 (exploratory): To identify predictors of parent adherence to *ImPACT Online* for the two treatment groups. This exploratory aim will be addressed using a multiple regression approach in which level of therapist support (self-directed versus therapist assisted) and three individual-level factors (computer and internet fluency, expectancies of treatment, and treatment acceptability) serve as primary predictors of parent adherence. We will also examine sociodemographic variables as predictors as well.

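### Aim 3 pairs its valid moderation test with a stress by time term pooled over all arms, leaves open which is followed up, and does not use the more powerful baseline-adjusted test at post-treatment

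*Combined protocol and SAP*

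**What the plan says.** The Aim 3 paragraph of the Statistical Analysis Plan opens with its objective: "To examine whether pre-treatment parenting stress moderates the effects of" the programme on parent fidelity and parent self-efficacy at post-treatment. It then sets out four steps.

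- Stress enters the Aim 1 multilevel model: "Pre-treatment parenting stress will be included in the MLM models as a covariate".
- The first interaction is stress by time: "The pre-treatment parenting stress by time interaction will be used to determine whether pre-treatment parenting stress moderates change over time, irrespective of treatment group".
- The second is the three-way term: "The three-way interaction of pre-treatment parenting stress, group, and time will be used to examine whether the relationship between group assignment" and change over time depends on stress.
- The follow-up rule is: "A significant interaction will be followed up by simple slopes analyses".

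Under Aim 1, time is categorical with three levels (pre-treatment, post-treatment, follow-up). Under Overall Approach, all randomised participants are analysed, so controls are in the model. Controls are offered the training only when the study is complete (Potential Benefits section).

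Under Parent Measures, the Parenting Stress Index is "a measure of parenting stress at pre-treatment". Self-efficacy is also a parent questionnaire: "Parents will complete the Parenting Sense of Competence Scale at pre-treatment, post-treatment, and follow-up". Fidelity is scored by the research team from video.

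**The concern.** A term averaged over trained and untrained parents describes who changes, not who benefits from training. The SAP uses this logic itself in Aim 1, where the time effect describes change across groups and only group by time compares them.

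The pooled term also need not be null when the training does nothing. Stress and self-efficacy are reported by the same parent at the pre-treatment assessment, and that assessment is a level of time in the model. A parent who enrols at a bad moment may score high on stress and low on self-efficacy, then drift back untrained. That drift appears as a stress by time interaction.

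If the pooled term is the one followed up, the trial could report that more stressed parents gain more, under an aim about the training, when untreated controls show the same pattern. The valid three-way test has limited power at N = 90, so the pooled term may well be the one that reaches significance.

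**Working it through.** **1. The plan's own figures.** The Power Analysis gives 80% power for fidelity (f = .32, r = .35) and 90% for self-efficacy (f = .25, r = .75) at N = 90. By the method described there, effective N = (90 - 3)/(1 - r²):

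- fidelity: 87/0.8775 = 99.1, power 80.9%
- self-efficacy: 87/0.4375 = 198.9, power 89.0%

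These use a three-group F test at an assumed alpha of .05, and both reproduce. They concern the effect of treatment condition. No power is given for any stress interaction.

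**2. The pooled term with no treatment effect.** Inputs from the documents are N = 90, three arms ("randomly assigned to the one of the three groups using random permuted blocks of 6", taken as 30 per arm), three visits, and r = .75 or .35, applied to every pair of visits. Two inputs are assumed: the correlation -k between stress and the baseline outcome, and the share s of that association that is specific to the pre-treatment visit.

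The correlation of stress with the later outcome is then -k(s·r + 1 - s). The expected slope of pre-to-post change on stress is k·s·(1 - r). The residual variance of change is 2(1 - r) less the squared slope. For self-efficacy with k = .5:

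- s = 1: slope .5 × .25 = .125; standard error √(.5 - .0156)/√90 = .0734; ratio 1.70; about 40% significant
- s = .5: slope .0625; standard error .0742; ratio 0.84; about 13%
- s = 0: slope 0; 5%

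Simulated percentages of trials with p < .05, testing the two changes from pre-treatment jointly:

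| Outcome | Correlation | s = 1 | s = .5 | s = 0 |
|---|---|---|---|---|
| Self-efficacy | -.5 | 39 | 12 | 5 |
| Self-efficacy | -.3 | 15 | – | – |
| Fidelity | -.3 | 35 | 11 | 5 |

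The three-way test stays at about 5% throughout.

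**3. Two valid tests of moderation compared.** Let stress modify the outcome by m SD per SD in both active arms and not in control, with stress unrelated to the baseline outcome. The slopes 0, m, m have squared deviations summing to (2/3)m², so the noncentrality is 30 × (2/3)m²/V. V is 2(1 - r) for change and 1 - r² with baseline as covariate. For m = .5 the numerator is 5:

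- fidelity: 5/1.30 = 3.85 against 5/0.8775 = 5.70
- self-efficacy: 5/0.50 = 10.0 against 5/0.4375 = 11.43

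On 2 and 84 degrees of freedom these give about 39% against 54%, and 80% against 85%. The simulation, which also lets stress vary from trial to trial, is slightly lower:

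| Outcome | m | Three-visit three-way test | Stress by group at post-treatment, baseline-adjusted |
|---|---|---|---|
| Fidelity | 0.3 | 14.5% | 21% |
| Fidelity | 0.5 | 37% | 50% |
| Self-efficacy | 0.3 | 33% | 38% |
| Self-efficacy | 0.5 | 78.5% | 82% |

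With no moderation, the baseline-adjusted test rejects in about 5% of trials.

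**The case against.** The strongest reply is that the correct test is already planned. The sentence after the pooled term specifies stress by group by time, which addresses the Aim 3 question and holds its error rate. A reader might infer from the order of the tests that Aim 3 rests on the pooled term, or that it has no valid moderation test. The documents support neither: order is not priority, and nothing lets the pooled term decide the aim.

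The pooled term is also openly labelled as ignoring group. Read that way, it asks a prognostic question. A significant result caused by regression to the mean correctly answers that question, so the percentages above are not type I error rates for it. They become errors only if the result is reported as moderation of the training effect. The SAP does not say it will be, and the follow-up rule can naturally be read as referring to the three-way term just before it.

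The size is conditional. The documents give neither the stress correlation nor its visit-specific share, and the 39% takes the extreme share. The same-reporter explanation fits self-efficacy but not video-scored fidelity, so the fidelity row in step 2 is arithmetic without a stated mechanism.

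Because time is categorical, the pre-to-post contrast of the three-way term is also available from the planned model. Including the follow-up visit is therefore not a flaw in itself.

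All of this stands. It leaves two things open: the pooled term sits under an aim solely about treatment moderation with an unspecified follow-up rule, and a more powerful test of that aim is available from data already collected.

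**Conclusion.** The point holds in limited form. Aim 3 includes a valid moderation test, but does not name it as the deciding one and does not say which interaction goes to simple slopes. The pooled term cannot answer the aim. Under no treatment effect its chance of significance for self-efficacy runs from 5% to about 39% at an assumed correlation of -.5, depending entirely on how much of the association belongs to the pre-treatment visit. That range shows what is possible and does not predict what this trial will find.

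The firmer gain is in the choice of test. With the plan's correlations, adjusting for baseline at post-treatment raises power by about 6 to 13 percentage points for fidelity and 3 to 5 for self-efficacy, at the same error rate. This assumes equal moderation in both active arms, no stress-baseline correlation, 30 per arm and no dropout. The fidelity gain is material and the self-efficacy gain small. Even with the better test, moderation of 0.3 SD would usually be missed.

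**What to change.** In the Aim 3 paragraph:

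1. Name one deciding test per outcome: stress by group at post-treatment, with the pre-treatment value of that outcome as covariate.
2. Limit simple slopes to the interaction that involves group.
3. Keep stress by time, if wanted, as a description by arm, with the control slope shown as the natural course. State the group coding: with the three-way term in the model and reference-arm coding, the stress by time coefficient refers to the reference arm and is not pooled.

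The change needs no new data. It has two costs. The pooled result is no longer available as an Aim 3 finding. Parents without a post-treatment visit also need a stated rule, because a single-visit analysis loses the partial records that the planned multilevel model uses. Either the EM imputation that the SAP already reserves for complete-data analyses is applied, or the test is taken as the post-treatment contrast from a multilevel model of the two later visits with the baseline outcome as covariate. The second option stays closer to the Aim 1 model.

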Protocol for Comparative Efficacy of Self-directed & Therapist-assisted Telehealth Parent
Training Intervention for Children With ASD

NCT02721381

Based on last approval by MSU IRB on 4/6/2020

Risk to Human Subjects

a. Human Subjects Involvement, Characteristics, and Design

A total sample of 90 children with ASD between the ages 18-96 months and their primary caregivers will be recruited for this study. This sample size was determined to be adequate for maintaining adequate power for the proposed statistical analyses, while allowing for some attrition.

Inclusion Criteria for Families: To be eligible for participation, 1) the child must receive a DSM-V-informed clinical diagnosis of Autism Spectrum Disorder, based on the *Autism Diagnostic Observation Schedule* (ADOS). The diagnosis may be provisional for children under age 3 (typically listed as "at risk for ASD"). Children with this classification will be included as well. (2) The child must fall between the ages of 18 - 96 months at enrollment into the study, which will allow for data collection during the period of early intervention and early childhood special education programming. (3) The parent must understand spoken English as the training materials are presented in English.

Exclusion Criteria for Families: (1) Children with ASD who have a history of significant brain injury or known neurological condition in addition to a diagnosis of ASD, significant sensory impairment or major medical problems. These children and their families may require very specific adaptations to the treatment and thus the results will not be representative of children with ASD. This will be determined through review of medical records, diagnostic reports and parent interview. Criteria and data sources for identifying participants are outlined below.

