Child Measures: Child diagnostic testing will be conducted at pre-treatment. We will also examine specific child characteristics (cognitive ability level, language level, autism severity) that are predicted to be related to the impact of the parent-implemented interventions. We will administer the Autism Diagnostic Observation Scale, 2nd Edition (ADOS-2) to the child at pre-treatment. The ADOS-2 is a standardized protocol for observation of social and communicative behavior associated with a diagnosis of ASD that has been shown to have high reliability and discriminant validity. Recent longitudinal studies have demonstrated that diagnostic stability for children under age 3 is best when using DSM-IV based clinical judgment in conjunction with results from standardized diagnostic instruments, such as the ADOS. As in previous studies, this is the approach that will be used in the present study in order to determine a specific DSM-V diagnosis for each child. The PI has established research reliability on the ADOS. She will train the clinical research staff on these methods (as needed) and supervise all assessments. Child cognitive ability will be assessed using the Mullen Scales of Early Learning at T1. Child intentional communication with the parent will be scored from a parent-child interaction in the home at pre-treatment and post-treatment using weighted frequency of intentional communication. Language outcomes will be assessed at pre-treatment and follow-up using the

Mullen Scales of Early Learning, a parent report measure (the MacArthur-Bates Communicative Development Inventory) and the Vineland Adaptive Behavior Scales.

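### Aim 4's fidelity model puts two concurrent, apparently same-session mediators in causal order, so its serial path can be significant when the programme has no effect on child communication

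*Combined protocol and SAP*

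**What the plan says.** Under Aim 4 the plan states: "We will conduct two serial mediation analyses using the PROCESS macro in SPSS". The first model asks whether "gains in parent fidelity (Mediator 1) and child intentional communication (Mediator 2) at post-treatment mediate the effect" of the programme on child outcomes at follow-up. The second replaces fidelity with self-efficacy: "gains in parent self-efficacy (Mediator 1) and child intentional communication (Mediator 2) at post-treatment".

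The sources of the scores are given under b. Sources of Materials:

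- Child Measures: "Child intentional communication with the parent will be scored from a parent-child interaction in the home at pre-treatment and post-treatment".
- Parent Measures: "Using the videotapes of the parent-child interaction in the home at pre-, post-treatment, and follow-up, the research team will assess parent use" of the trained strategies.
- Parent Measures, for self-efficacy: "Parents will complete the Parenting Sense of Competence Scale at pre-treatment, post-treatment, and follow-up to assess parent self-efficacy".

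No second home interaction, earlier fidelity time point or separate coding segment is described. Only the language outcome, at the 3-month follow-up, is separated in time from the mediators. Aim 1 tests parent outcomes and Aim 2 tests verbal language. Child intentional communication enters the analysis plan only as Mediator 2.

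**The concern.** A serial model takes Mediator 1 to precede and influence Mediator 2. Here the two are concurrent and, in the fidelity model, apparently come from the same interaction. A child who initiates more gives the parent more openings to use the strategies, and a poor session lowers both scores. Either mechanism produces a positive fidelity-to-communication coefficient that owes nothing to the parent's effect on the child.

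If the programme raises fidelity, and communicative children later have better language, the product of the three links is then positive even when the arms do not differ on any child measure. Only Aim 5 is labelled exploratory, so Aim 4 would be read as the trial's evidence on mechanism. As written, it could report a route through the child that does not exist.

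**Working it through.** **Inputs from the documents.** The sample is "A total sample of 90 children with ASD between the ages 18-96 months", "randomly assigned to the one of the three groups using random permuted blocks of 6", taken as 90 / 3 = 30 per arm. Power Analysis gives f = .32 and r = .35 for fidelity, and r = .65 between pretest and follow-up language.

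**Assumed, because the documents do not give them.** Two-sided alpha .05; a within-arm fidelity-communication correlation ρ, not caused by the parent, of 0 to .5; a communication-language slope b of .2 to .5.

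**Step 1: the plan's own figures.** For f = .32, three groups and 80% power, the sample without a covariate is 98. The plan's adjustment gives 98 × (1 − .35²) + 3 = 98 × .8775 + 3 = 89.0, and power at 90 is 80.9%. The fidelity figure reproduces. The figure of about 90% for Aims 2 and 4 concerns the effect of treatment condition, not an indirect path. By the same method it needs 206 × (1 − .65²) + 3 = 122.0 participants, and power at 90 is 78.1%. That is a separate matter, and nothing below depends on it.

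**Step 2: effect on fidelity.** With equally spaced arm means 0, δ/2, δ and unit within-arm SD, f = δ/√6. So δ = .32 × √6 = 0.784 for therapist-assisted against control.

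**Step 3: what the serial model estimates under the null.** Let X compare therapist-assisted with control. Let M1 = δX + e1, M2 = e2 with corr(e1, e2) = ρ, and Y = bM2 + error. Neither group nor fidelity affects communication or language.

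- Group to M1: δ.
- M1 to M2, given group: ρ.
- Group to M2, given M1: −δρ.
- M2 to Y: b.
- Serial path: δρb. Path group → M2 → Y: −δρb. The two sum to zero.

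At ρ = .3, b = .3 the serial path is .784 × .3 × .3 = .071; the simulated means of the two paths were .071 and −.067. At ρ = .5, b = .5 it is .784 × .5 × .5 = .196; the simulated means were .203 and −.202.

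**Step 4: how often the serial path is significant under this null.**

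| ρ | A: single scores, 60 v 30 | B: single scores, three arms | C: gain scores, three arms |
|---|---|---|---|
| 0 | 1-5% | 1.3-1.7% | 1.8-2.2% |
| .1 | 6-16% | not run | 8-17% |
| .2 | 23-45% | 30-40% | 21-38% |
| .3 | 38-78% | 49-69% | 34-65% |
| .4 | not run | 60-83% | 41-86% |
| .5 | 42-92% | 60-87% | not run |

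- A counts trials with all three links significant; fidelity d .5 to .9, b = .3 to .4.
- B counts trials whose 95% percentile bootstrap interval lies above zero (nominal 2.5%); δ = .784, b = .3 and .5, 300 trials per setting.
- C uses the same interval and δ. Mediators are post-minus-pre gains that share only session noise, and language is adjusted for its pretest at r = .65. The loading of language on true child change is .2 to .4, with 400 trials per setting.

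Simulation error at 50% is √(.25/300) = 2.9 points in B and √(.25/400) = 2.5 points in C.

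**Step 5: which additions help.**

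- In the parallel model the communication equation omits fidelity, so its group coefficient is the total randomised effect. The communication path was positive in about 1-3% of null trials.
- The reverse chain (communication, then fidelity, then language) was significant in at most 0.4% of null trials, because its first link is truly zero.
- Also requiring a significant group effect on communication cut false chains to 0-4.3% in version B. Under a true chain (fidelity-to-communication .3 to .5, fidelity d .5 to .9) it cut detection from 48-92% to 5-48%. A second run gave 41-90% falling to 5-39%.

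**The case against.** **One recording is not stated.** One passage refers to a home interaction and the other to videotapes of the home interaction. Neither gives the number of recordings, tasks, segments or coders. A reader might infer that the same minutes of video are documented as the source of both scores. They are not; that is only the natural reading. This stands, and the overlap should be called apparent. That both mediators are measured at post-treatment is explicit.

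**The plan does not claim a causal link in words.** It says only that the analyses examine mediation. A reader might infer that the plan commits itself to reading the middle link as causal. The text does not say so. The causal order is implied by the choice of serial model, and no rule for interpretation is given either way.

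**A null programme would show elsewhere.** Aim 2 tests the randomised effect on language, and the serial regressions contain an offsetting direct path. This is a partial safeguard. However, Aim 4 is not made conditional on Aim 2, Aim 2 does not test communication, and a serial path can be reported without attention to the path that cancels it.

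**The sizes rest on assumptions.** This stands. No document supports any ρ or slope, and at ρ = .1 the excess is modest. The simulations also treat all of the within-arm correlation as artefact, with none due to real parent influence.

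**Scope.** A reader might extend the shared-session argument to both Aim 4 models. Self-efficacy is a questionnaire, so the argument covers only the fidelity model. The second model shares only the concurrency of its mediators.

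**Conclusion.** The point holds as a limit on what Aim 4 can conclude. The order of concurrent mediators cannot be recovered from these data, and in the fidelity model a significant serial path is not by itself evidence that the programme acts through child communication. The size depends on three conditions: a real effect on fidelity, a within-arm correlation not caused by the parent, and an association between communication and later language. A shared-session correlation of .2 is enough to raise the false-chain rate to between about one in five and a little under one in two. At zero correlation there is no material inflation.

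The documents do not support a stronger conclusion that the mediation result will be false, or that the trial's other aims are affected. Aims 1 and 2 rest on randomised comparisons and are untouched.

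**What to change.** Amend Aim 4 as follows:

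1. Estimate the total randomised group effect on post-treatment child intentional communication, adjusted for its pre-treatment value, and report it with a confidence interval.
2. Report the unordered (parallel) two-mediator model beside the serial one.
3. State for both Aim 4 models that the mediators are concurrent, so the link from Mediator 1 to communication is an association. State also that a positive serial path without a group difference in communication is not evidence that the programme works through the child.

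Three further measures may suggest themselves but are not recommended. A significance requirement on the group effect on communication gives up too much power for a true chain. A reverse-order comparison would almost always fail under the null and so falsely favour the planned order. Scoring the mediators from separate segments would leave session-level mood in both scores.

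The cost is SAP wording and a few extra model runs on scores already planned, with no new visits or participants. The downside is a weaker mechanism claim.
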